9.4.4 Clinical Laboratory

9.4.4.1 Hematology, Serum Chemistry, Coagulation

Blood samples will be collected for coagulation at screening, and hematology and serum chemistry, throughout the study. Analytes to be evaluated are summarized in [Table 15](#).

All blood samples will be sent to the central laboratory. Subjects may be considered eligible for the study based on results reported by a local laboratory; however, screening samples must also be sent to the central laboratory. Both local and central screening laboratories must adhere to the visit window provided in [Appendix A](#).

Table 15: Summary of Laboratory Analytes

Hematology	Complete blood count (red blood cells, white blood cells with differentiation and absolute values, hemoglobin, hematocrit, reticulocytes, and platelets)
------------	--

Statistical Analysis Plan (Methods)
Study 547-PPD-304Sage Therapeutics, Inc.
CONFIDENTIAL

Coagulation (at Screening only)	Activated partial thromboplastin time, prothrombin time, and international normalized ratio
Biochemistry	Serum electrolytes (sodium, potassium, chloride, bicarbonate or total carbon dioxide, calcium, and phosphorus) renal function tests (creatinine and blood urea nitrogen); liver function tests (total bilirubin, alkaline phosphatase, aspartate aminotransferase, alanine aminotransferase, and gamma glutamyl transferase); thyroid stimulating hormone; total protein; albumin and glucose (fasting or non-fasting)

All clinical laboratory test results outside the reference range will be interpreted by the Investigator as abnormal, not clinically significant; or abnormal, clinically significant (CS). Screening results considered abnormal and CS at the Screening Visit may make the subject ineligible for the study pending review by the Investigator or Medical Monitor. Clinically significant abnormal results after screening will be considered and reported as AEs.

Summary tables will include descriptive statistics for the actual values and changes from baseline by scheduled time point in hematology, serum chemistry, and coagulation by treatment group. Frequency counts and percentages will be presented over time for these categorical data by treatment.

Shift analysis pre- and post-treatment will be presented for the following laboratory categories (low, normal and high).

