Number and percent of subjects with liver injury as defined by Hy's law will be presented. Hy's law is defined as ALT or AST > 3 times of upper limit of normal; and total bilirubin > 2 times of upper limit of normal, and alkaline phosphatase < 2 time of upper limit of normal.

All parameters will be converted to consistent units according to the International System of Units (SI) before summarization.

All clinical laboratory results will be listed by subject and timing of collection. Out-of-range values will be flagged as low, high, or abnormal, where applicable.

The number and percentage of subjects with potentially clinically significant (PCS) values at any time after study drug infusion will be summarized by treatment group for the hematology and chemistry parameters defined in [Table 16](#) and [Table 17](#). PCS laboratory values will also be listed by subject.

Statistical Analysis Plan (Methods)
Study 547-PPD-304Sage Therapeutics, Inc.
CONFIDENTIAL**Table 16: Hematology Potentially Clinically Significant Values**

Laboratory Parameter	Sex	Units	Criteria for PCS Values (Observed values)	
			High	Low
Hemoglobin	Male	g/L	>185	<115
	Female	g/L	>170	<100
Hematocrit	Male	Fraction of 1	>0.55	<0.385
	Female	Fraction of 1	>0.49	<0.345
Platelet count		10 ⁹ /L	>600	<125
White blood cell		10 ⁹ /L	>15	<2.5
Basophils		10 ⁹ /L	>0.5	NA
Eosinophils		10 ⁹ /L	>1.5	NA
Neutrophils		10 ⁹ /L	NA	<1.5
Lymphocytes		10 ⁹ /L	>6.0	<0.5
Monocytes		10 ⁹ /L	>1.4	NA

Abbreviations: PCS = Potentially Clinically Significant

Statistical Analysis Plan (Methods)
Study 547-PPD-304Sage Therapeutics, Inc.
CONFIDENTIAL**Table 17: Chemistry Potentially Clinically Significant Values**

Laboratory Parameter	Units	Criteria for PCS Values (Observed values)	
		High	Low
Albumin	g/L	>70	<28
Blood urea nitrogen	mmol/L	>10.71	NA
Calcium	mmol/L	>2.75	<2.0
Chloride	mmol/L	>120	<90
Creatinine	mmol/L	>3xULN or >3x Baseline	
Gamma Glutamyl Transferase		>3xULN	
Glucose	mmol/L	>13.9	<2.8
Sodium	mmol/L	>150	<132
Potassium	mmol/L	>5.4	<3.3
Protein	g/L		<45
Bicarbonate	mmol/L	>34	<18
Chloride	mmol/L	>120	<90
Phosphorus	mmol/L	>1.94	<0.61
Liver Function Tests (LFT)			
Bilirubin	µmol/L	>2xULN	NA
Aspartate Aminotransferase	U/L	>3xULN	NA
Alanine Aminotransferase	U/L	>3xULN	NA
Alkaline Phosphatase	U/L	>1.5xULN	NA

Abbreviations: PCS = Potentially Clinically Significant

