Liver function tests will be monitored closely for potentially clinically significant values, and will be summarized for occurrence any time post-baseline for the following parameters for these PCS threshold (for condition involving >1 parameter, the results need to be from the same timepoint):

Alanine Aminotransferase: >3xULN, >5xULN, >10xULN

Aspartate Aminotransferase: >3xULN, >5xULN, >10xULN

Alanine Aminotransferase or Aspartate Aminotransferase: >3xULN, >5xULN, >10xULN

Alkaline Phosphatase: >1.5xULN, >2xULN

Total Bilirubin: >1.5xULN, >2xULN

Total Bilirubin > 2xULN AND (Alanine Aminotransferase or Aspartate Aminotransferase >3xULN)

Statistical Analysis Plan (Methods)
Study 547-PPD-304

Sage Therapeutics, Inc.
CONFIDENTIAL

Total Bilirubin >2xULN AND Alkaline Phosphatase >2xULN AND (Alanine Aminotransferase or Aspartate Aminotransferase >3xULN)

Any lab results considered clinically significant by the investigator will be captured as AEs events, hence will show up in AE displays.

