9.4.5 Electrocardiogram

A baseline 12-lead ECG will be performed during screening. The following ECG parameters will be recorded: heart rate (bpm), pulse rate (PR) (msec), QRS (msec), QT (msec), and QT corrected with Fridericia's formula (QTcF) (msec).

QTcF (msec) is calculated as: QT (msec) / $RR^{1/3}$, where $RR = 60 / \text{heart rate (bpm)}$.

All ECG results will be interpreted by the Investigator as 'normal' 'abnormal, NCS'; or 'abnormal, CS'. If 'abnormal', details will be provided.

The actual value at each time point and change from baseline at each post-baseline time point will be summarized by treatment group. The number and percentage of subjects with 'normal', 'abnormal, not clinically significant' and 'abnormal, clinically significant' ECG results will be summarized at baseline and each post-baseline time point.

All ECG data will be listed by subject and time of measurement. Mean values of ECG parameters over time will be presented graphically by treatment group.

Additionally, the number and percentage of subjects with PCS and potentially clinically significant change (PCSC) values will be summarized for such occurrence any time post-baseline. Potentially clinically significant values will be identified for ECG parameters as outlined in the following table. This analysis includes triplicate values individually and is not based on average value. In addition, any PCS value at any time post-baseline will be summarized as shown in [Table 18](#).

Table 18: ECG Potentially Clinically Significant Values

ECG	Units	Criteria for PCS Values (Observed values)		Criteria for PCSC values (Change from Baseline)	
		High	Low	Increase	Decrease
QTcF Interval	msec	>450 but \leq 480 >480 but \leq 500 >500	NA	\geq 30 to 60 >60	NA

Abbreviations: PCS = Potentially Clinically Significant; PCSC = Potentially Clinically Significant Change; NA=Not Available

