9.4.6 Vital Signs

Vital signs include oral temperature (°C), respiratory rate (breaths/min), heart rate (bpm), and blood pressure (mmHg). Heart rate and blood pressure to be collected in supine position at all scheduled time points as well as in the standing position at specific time points listed in [Appendix A](#). A full set of vital signs will be obtained at all specified time points (± 30 minutes), unless the subject is asleep between the hours of 23.00 h and 06.00 h.

Additionally, respiratory rate, heart rate, and blood pressure should be collected for any subject that experiences an AESI as soon as is feasible after the onset of the event and recorded as unscheduled in the eCRF. Collection of vital signs should occur per local clinical practice, at a minimum until the subject regains consciousness.

Additionally, the number and percentage of subjects with PCS and PCSC values will be summarized for such occurrence any time post-baseline. Potentially clinically significant values will be identified for vital sign parameters as outlined in the [Table 19](#).

Statistical Analysis Plan (Methods)
Study 547-PPD-304Sage Therapeutics, Inc.
CONFIDENTIAL**Table 19: Vital Signs Potentially Clinically Significant Values**

Vital Sign	Units	Criteria for PCS Values (Observed values)		Criteria for PCSC values (Change from Baseline values)	
		High	Low	Increase	Decrease
Heart rate (supine and standing)	Beats/min	>120	<40	NA	NA
Systolic Blood Pressure (supine and standing)	mmHg	>180	<90	≥30	≥30
Diastolic Blood pressure (supine and standing)	mmHg	>110	<50	≥20	≥20
Supine - Standing Systolic Blood Pressure	mmHg	≥20			
Supine – Standing Diastolic Blood Pressure	mmHg	≥10			

PCS = Potentially Clinically Significant; PCS = Potentially Clinically Significant Change; NA=Not Available

The change from supine to standing (Supine – Standing) vital signs – heart rate, systolic and diastolic blood pressure – will be summarized by scheduled assessment timepoint.

Any vital signs results considered clinically significant by the investigator will be captured as adverse events, hence will show up in AE displays.

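### The observed-value PCS summaries do not separate abnormalities present before dosing from new ones, and the lab rule words its counting period differently from the others

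*SAP*

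**What the plan says.** Four rules in the SAP count subjects with potentially clinically significant (PCS) values.

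- **Hematology and chemistry (Section 9.4.4.1, Tables 16 and 17).** Subjects are counted if they have "potentially clinically significant (PCS) values at any time after study drug infusion will be summarized by treatment group". The limits appear under the column title "Criteria for PCS Values (Observed values"). Creatinine alone has a baseline-relative alternative: ">3xULN or >3x Baseline".
- **Liver tests (Section 9.4.4.1, list after Table 17).** A further set of thresholds "will be summarized for occurrence any time post-baseline for the following parameters".
- **ECG (Section 9.4.5, Table 18).** "In addition, any PCS value at any time post-baseline will be summarized as shown in" that table. QTcF also has change-from-baseline (PCSC) categories.
- **Vital signs (Section 9.4.6, Table 19).** Here "the number and percentage of subjects with PCS and PCSC values will be summarized for such occurrence any time post-baseline". Systolic and diastolic pressure have PCSC limits. For heart rate the PCSC entry is NA, and the supine-minus-standing criteria have no change limit.

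Baseline also enters through the lab shift tables: "Shift analysis pre- and post-treatment will be presented for the following laboratory categories (low, normal and high"). Section 9.1.2 defines baseline as the last non-missing value before study drug starts, so each subject with a baseline value can be classified against every PCS limit.

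**The concern.** A subject who is beyond a limit before dosing and stays there unchanged is counted in the post-baseline PCS table exactly like a subject who crosses the limit after dosing. The table alone does not tell the two apart. This differs from the SAP's treatment of adverse events, where Section 9.4.2 admits a pre-existing condition only if it worsens after the infusion starts.

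The distinction matters more here than in a fully controlled trial. Under Section 6.1 every Version 4 subject receives brexanolone, so for those subjects no concurrent arm shows how often a limit is exceeded without the drug. Section 6.2 plans 20 treated subjects, so a single pre-existing case moves a percentage visibly.

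A second, smaller issue is the counting period. The hematology and chemistry rule refers to the time after the infusion without saying whether its start or its end is meant. The other three rules say post-baseline. ALT, AST, bilirubin and alkaline phosphatase are tabulated at identical thresholds under both laboratory rules, so the same row is produced twice under two differently worded periods.

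**Working it through.** **1. Where baseline enters, and what is left uncovered**

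| Feature in the SAP | What it does | What it leaves open |
|---|---|---|
| Low/normal/high lab shifts (9.4.4.1) | Baseline against post-treatment category | For a PCS limit outside the reference range, a persistent PCS value and a new PCS value in a subject already mildly low both read as low to low |
| Creatinine alternative (Table 17) | Flags a rise relative to baseline | It is an alternative to the ULN limit, not a condition on it; no other analyte has one |
| PCSC for QTcF and blood pressure (Tables 18, 19) | Flags change from baseline | Tabulated separately from PCS; does not show who was already PCS; none for heart rate or the supine-minus-standing criteria |
| Investigator's ECG reading at baseline and each later time point (9.4.5) | Shows background of abnormal readings | Uses the reader's category, not the QTcF limits |
| Listings (9.4.4.1, 9.4.5) | Allow case-by-case checking | Not reflected in the tabulated percentage |

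**2. Scale**

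The SAP gives no figure to reproduce: Section 6.2 states that there is no formal sample size calculation, and no baseline PCS rate appears anywhere. The rates below are therefore assumptions, shown as a range.

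Inputs: N = 20 (Section 6.2); assumed baseline prevalence *b* for one criterion; assumed persistence *s* from 50% to 100%.

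Expected pre-existing cases counted = N × b × s. Probability of at least one = 1 − (1 − b × s)^20. One subject = 100/20 = 5 percentage points.

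| b | b × s | Expected of 20 | P(at least one) |
|---|---|---|---|
| 5% | 0.025 to 0.05 | 0.5 to 1.0 | 1 − 0.975^20 = 0.40 to 1 − 0.95^20 = 0.64 |
| 10% | 0.05 to 0.10 | 1.0 to 2.0 | 0.64 to 1 − 0.90^20 = 0.88 |
| 20% | 0.10 to 0.20 | 2.0 to 4.0 | 0.88 to 1 − 0.80^20 = 0.99 |

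A made-up example shows the effect on a table row. Suppose 2 of 20 subjects are PCS at baseline and remain so, and 1 other becomes PCS after dosing. The planned row shows 3/20 = 15%. Split, it shows 2/20 = 10% at baseline and 1/18 = 5.6% new.

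**3. The counting period**

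- The infusion lasts 60 hours (Section 6.1).
- Post-dose labs are scheduled at Hour 72 and Day 14 (Table 11, Appendix A). Both fall after Hour 60, so no scheduled lab lies within the infusion and all scheduled results count under either wording.
- Unscheduled and early-termination results are eligible for analysis windows (Section 9.3.3, applied to safety by Section 9.4.1), and Table 11's first post-dose window opens just after Hour 0. A sample drawn during the infusion would therefore be post-baseline. It would be excluded from Tables 16 and 17 only if the period is read as beginning when the infusion ends.
- Overlap of the two laboratory rules: ALT above 3×ULN, AST above 3×ULN, bilirubin above 2×ULN and alkaline phosphatase above 1.5×ULN. For these four the tables could disagree on such a sample.

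**The case against.** The strongest reply is that counting any post-baseline PCS value is an accepted convention in descriptive safety summaries and that nothing in the SAP is misstated. This stands: the first issue is a weakness of interpretation, not an error. It is also true that, with about 20 subjects, the listings let a reader trace each case, and that Section 3 presents Version 1 to 3 subjects by randomized arm, so some placebo data exist. These help, but they leave the tabulated percentage mixed and give Version 4 subjects no concurrent comparison.

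A reader might infer more than the document supports, in four ways.

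- *That the PCS analyses ignore baseline altogether.* They do not: QTcF and blood pressure have PCSC criteria, creatinine has its baseline multiple, and labs have change-from-baseline summaries and shift tables.
- *That the primary endpoint is affected.* Section 5.1 makes this the incidence of TEAEs, which is treatment-emergent by definition. The PCS tables are supportive, and lab results that the investigator judges clinically significant are reported as adverse events in any case.
- *That a known share of the PCS counts is spurious.* The SAP gives no prevalence, and one rate would not suit limits as different as ALT above 3×ULN and a low hematocrit. Clinically significant screening abnormalities may also lead to exclusion.
- *That labs taken during the infusion will be lost.* None is scheduled then. A loss needs an unscheduled or early-termination sample beyond a limit, no later sample beyond it, and the end-of-infusion reading. Section 9.4.3 uses *prior to the infusion* for before its start, which points to the other reading.

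It is also fair that restricting the count to subjects without the abnormality at baseline would hide worsening within a criterion. That is a reason to keep the planned count, not to omit the split.

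**Conclusion.** The point holds in a limited form. The observed-value PCS counts in Tables 16 to 19 and in the liver list do not distinguish pre-existing from new abnormalities, and the other baseline-related displays close that gap only in part. Each unchanged pre-existing case adds 5 percentage points to a row when N is 20. How many such cases there will be depends on baseline rates that the SAP does not give; the range from 0.5 to 4 per criterion rests wholly on assumed prevalences of 5% to 20% and persistence of 50% to 100%. This makes the change a cheap improvement to how the uncontrolled percentages can be read, not the correction of an error.

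The difference in counting period is real in the wording and includes four liver analytes at the same thresholds. Its practical reach is confined to unscheduled or early-termination labs drawn during the 60 hours, and only on the literal end-of-infusion reading.

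**What to change.** 1. For each observed-value PCS criterion in Tables 16 to 19 and the liver list, keep the planned all-subject post-baseline count and show beside it (a) the number already meeting the same criterion at baseline, as defined in Section 9.1.2, and (b) the number and percentage newly meeting it among subjects who did not meet it at baseline. State how subjects without a baseline value are shown.
2. In the hematology and chemistry rule of Section 9.4.4.1, let the period run from the *start* of study drug infusion, so that it matches the liver, ECG and vital sign rules and the four shared liver rows use one period.

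**Cost.** SAP wording and one baseline flag per criterion; no new data. The new-onset percentage has a denominator that differs by criterion and can fall below 20, so it should be printed in each row. Worsening in a subject who already met the criterion at baseline will be visible only in the all-subject count and the listings, which is why both stay.

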9.4.4.2 Hormones and Exploratory Biochemistry

Blood samples will be collected and may be analyzed for estrogen, progesterone, progesterone metabolites, oxytocin, tryptophan, kynurenone, and markers of inflammation.

9.4.4.3 Pregnancy Test

All subjects will be tested for pregnancy by serum human chorionic gonadotropin (HCG) at the Screening Visit and by serum or urine HCG at other scheduled time points. Subjects may be considered eligible for the study based on serum pregnancy test results reported by a local laboratory; however, screening samples must also be sent to the central laboratory. Subjects with a positive pregnancy test at screening or Day 1 will be ineligible for study participation. Pregnancy test results will be listed by subject.

9.4.4.4 Drugs of Abuse and Alcohol

Urine assessment for select drugs of abuse will be performed (including amphetamines, barbiturates, benzodiazepines, cannabinoids, cocaine, opiates, and phencyclidine). A positive urine drug screen is exclusionary, unless deemed by the investigator to reflect a prescribed medication. Alcohol will be assessed via breathalyzer or urine dipstick. Drug screening and alcohol assessment results will be listed.

9.4.5 Electrocardiogram

A baseline 12-lead ECG will be performed during screening. The following ECG parameters will be recorded: heart rate (bpm), pulse rate (PR) (msec), QRS (msec), QT (msec), and QT corrected with Fridericia's formula (QTcF) (msec).

QTcF (msec) is calculated as: QT (msec) / $RR^{1/3}$, where $RR = 60 / \text{heart rate (bpm)}$.

All ECG results will be interpreted by the Investigator as 'normal' 'abnormal, NCS'; or 'abnormal, CS'. If 'abnormal', details will be provided.

The actual value at each time point and change from baseline at each post-baseline time point will be summarized by treatment group. The number and percentage of subjects with 'normal', 'abnormal, not clinically significant' and 'abnormal, clinically significant' ECG results will be summarized at baseline and each post-baseline time point.

All ECG data will be listed by subject and time of measurement. Mean values of ECG parameters over time will be presented graphically by treatment group.

Additionally, the number and percentage of subjects with PCS and potentially clinically significant change (PCSC) values will be summarized for such occurrence any time post-baseline. Potentially clinically significant values will be identified for ECG parameters as outlined in the following table. This analysis includes triplicate values individually and is not based on average value. In addition, any PCS value at any time post-baseline will be summarized as shown in [Table 18](#).

Table 18: ECG Potentially Clinically Significant Values

ECG	Units	Criteria for PCS Values (Observed values)		Criteria for PCSC values (Change from Baseline)	
		High	Low	Increase	Decrease
QTcF Interval	msec	>450 but \leq 480 >480 but \leq 500 >500	NA	\geq 30 to 60 >60	NA

Abbreviations: PCS = Potentially Clinically Significant; PCSC = Potentially Clinically Significant Change; NA=Not Available

9.4.6 Vital Signs

Vital signs include oral temperature (°C), respiratory rate (breaths/min), heart rate (bpm), and blood pressure (mmHg). Heart rate and blood pressure to be collected in supine position at all scheduled time points as well as in the standing position at specific time points listed in [Appendix A](#). A full set of vital signs will be obtained at all specified time points (± 30 minutes), unless the subject is asleep between the hours of 23.00 h and 06.00 h.

Additionally, respiratory rate, heart rate, and blood pressure should be collected for any subject that experiences an AESI as soon as is feasible after the onset of the event and recorded as unscheduled in the eCRF. Collection of vital signs should occur per local clinical practice, at a minimum until the subject regains consciousness.

Additionally, the number and percentage of subjects with PCS and PCSC values will be summarized for such occurrence any time post-baseline. Potentially clinically significant values will be identified for vital sign parameters as outlined in the [Table 19](#).

Statistical Analysis Plan (Methods)
Study 547-PPD-304Sage Therapeutics, Inc.
CONFIDENTIAL**Table 19: Vital Signs Potentially Clinically Significant Values**

Vital Sign	Units	Criteria for PCS Values (Observed values)		Criteria for PCSC values (Change from Baseline values)	
		High	Low	Increase	Decrease
Heart rate (supine and standing)	Beats/min	>120	<40	NA	NA
Systolic Blood Pressure (supine and standing)	mmHg	>180	<90	≥30	≥30
Diastolic Blood pressure (supine and standing)	mmHg	>110	<50	≥20	≥20
Supine - Standing Systolic Blood Pressure	mmHg	≥20			
Supine – Standing Diastolic Blood Pressure	mmHg	≥10			

PCS = Potentially Clinically Significant; PCS = Potentially Clinically Significant Change; NA=Not Available

The change from supine to standing (Supine – Standing) vital signs – heart rate, systolic and diastolic blood pressure – will be summarized by scheduled assessment timepoint.

Any vital signs results considered clinically significant by the investigator will be captured as adverse events, hence will show up in AE displays.

